## **5.4 Post-Treatment Period**

### **5.4.1 Post-Treatment Follow-Up Visit**

Subjects who discontinue from study treatment will return to the site 30 (+14) days after the date of the decision to discontinue study treatment. During the Post-Treatment Follow-Up Visit, safety assessments will be performed. Please refer to Appendix A for a description of all the assessments at this visit. (Assessments in the Post-Treatment period for subjects who discontinue study treatment in the Crossover Phase are provided in Appendix B.)

Adverse events are to be documented and/or followed as described in Section 8.3.

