## 8 SAFETY

### 8.1 Adverse Events and Laboratory Abnormalities

An AE is any untoward medical occurrence in a patient or clinical investigation subject who has been enrolled in a clinical study and who may have been administered an investigational product, regardless of whether or not the event is assessed as related to the study treatment. An AE can therefore be any unfavorable and unintended sign (including an abnormal laboratory finding), symptom, or disease temporally associated with the use of an investigational product, regardless of whether or not the event is assessed as related to the investigational product. This definition also includes events associated with medication errors and uses of the investigational product outside of what is in the protocol, including misuse and abuse. Preexisting medical conditions that worsen during a study should be recorded as AEs. Abnormal laboratory values, ECG findings, or vital signs are to be recorded as AEs if they meet the criteria described in Section 8.3.

All untoward events that occur after informed consent through 30 days after the date of the decision to discontinue study treatment are to be recorded by the investigational site. At each scheduled and unscheduled visit, AEs are to be identified and assessed based upon study procedures, routine and symptom-directed clinical investigations, and subject query/report.

Assessment of the relationship of the AE to the study treatment by the investigator will be based on the following two definitions:

- **Not Related**: An event is assessed as not related to study treatment if it is attributable to another cause and/or if there is no evidence to support a causal relationship.
- **Related**: An event is assessed as related to study treatment when there is a reasonable possibility that the study treatment caused the event. Reasonable possibility means there is evidence to suggest a causal relationship between the drug and the event. This event is called a suspected adverse reaction. A suspected adverse reaction implies a lesser degree of certainty about causality than adverse reaction, which means any AE caused by a drug.

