| Survival, post-study treatment (Section 5.4 and 5.7.11)                    |   |   |             |             |             |             |                      |   | Every 12 wks       |

CAPN, chest/abdomen/pelvis/neck; CRF, case report form; CT, computed tomography; ECG, electrocardiogram; ECOG, Eastern Cooperative Oncology Group; ICF, informed consent form; IRB/EC, Institutional Review Board/Ethics Committee; MRI, magnetic resonance imaging; PT/INR, prothrombin time/international normalized ratio; PTT, partial thromboplastin time; RECIST, Response Evaluation Criteria in Solid Tumors; UPCR, urine protein/creatinine ratio.

- a Screening assessments must be reviewed by the investigator before crossover to confirm that the subject meets the crossover eligibility criteria. Only subjects randomized to the placebo arm who opt to crossover to receive cabozantinib will undergo crossover screening. Subjects randomized to the cabozantinib arm and subjects randomized to the placebo arm who do not crossover will continue their original study assessments per Appendix A according to the Week and Day from time of first dose of blinded treatment.
- b In addition to informed consent obtained for the main study, informed consent specific for the Crossover Phase must be obtained. Informed consent may be obtained greater than 28 days prior to crossover, but must be provided before any study-specific procedures are performed; however evaluations performed as part of routine care prior to informed consent can be utilized as screening evaluations if permitted by the site's IRB/EC policies. The Investigator must ensure that the subject consents on the most recent version of the ICF.
- c Interval medical history will be collected for subjects randomized to the placebo arm who undergo screening for crossover and who have discontinued blinded study treatment > 30 days prior to W1D1 of crossover. All adverse events that were experienced ≤ 30 days after the date of decision to discontinue any study treatment (blinded or unblinded) will be collected on the adverse event CRF.
- d Additional ECGs should be performed if clinically indicated

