**Table 3: Schema for Efficacy Summaries**

|                             |  |  |
|-----------------------------|--|--|
| Treatment Period:    | Blinded Period   |  |
| Group:               | Subjects randomized to cabozantinib (Cabozantinib arm) | Subjects randomized to placebo (Placebo arm) |
| Start Date of Period | Randomization Date                                     |  |

Safety summaries (adverse events, exposure, etc.) will be categorized in the following groups:

- (a) Subjects randomized to and treated with cabozantinib (Cabozantinib arm),
- (b) Subjects randomized to placebo but receiving cabozantinib after crossover (Placebo crossover arm),
- (c) Subjects who received cabozantinib at any time, i.e., subjects randomized to and receiving cabozantinib, and the subjects randomized to placebo and receiving cabozantinib after crossover, and
- (d) Subjects randomized to and receiving placebo until crossover or end of treatment

Table 4: Schema for Safety Summaries

| Treatment:            | Cabozantinib  |  |   | Placebo  |
|------------------------------|--|--|---|---|
| Group:                | Subjects randomized to and receiving cabozantinib (Cabozantinib arm)  | Subjects randomized to placebo but receiving cabozantinib after crossover (Placebo crossover arm)   | All subjects receiving cabozantinib including crossover subjects (All Cabozantinib arm)  | Subjects randomized to and receiving placebo (Placebo arm)   |
| Start Date of Period: | Date of 1 st dose of cabozantinib   | Date of 1 st dose of cabozantinib after crossover   | Date of 1 st dose of cabozantinib  | Date of 1 st dose of placebo   |
| End Date Of Period:   | Earlier of the date of last date of exposure to cabozantinib+30 days, or date of withdrawal of consent by subject, or date of death, or date of data cut-off | Earlier of the last date of exposure to open-label cabozantinib +30 days, or date of withdrawal of consent by subject, or date of death, or date of data cut-off | Earlier of the last date of exposure to cabozantinib +30 days, or date of withdrawal of consent by subject, or date of death, or date of data cut-off | Earlier of the last date of exposure to placebo, or date of withdrawal of consent by subject, date of death, or date of receipt of open-label cabozantinib -1, or date of data cut-off. |

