#### **4.6 Safety Observation Period**

The safety observation period is defined as follows for the summaries described above in Section 4.1:

The safety observation period for subjects randomized to and receiving any cabozantinib is defined as the time between the date of first dose of cabozantinib to the earlier of the date of last dose of cabozantinib +30 days, or date of withdrawal of consent by subject, or date of death, or date of data cut-off.

The safety observation period for all subjects receiving placebo only during the blinded treatment period is defined as the time between the date of first dose of placebo to the earlier of the date of last dose of placebo, or date of withdrawal of consent by subject, date of death, or date of receipt of open-label cabozantinib -1, or date of data cut-off.

Subjects crossing over from placebo to cabozantinib will have data from the crossover period summarized independently. The post-crossover safety observation period of all subjects receiving cabozantinib after crossing over from placebo is defined as the time between the date of first dose of open-label cabozantinib to the earlier of the date of last dose of open-label study treatment +30 days, or date of withdrawal of consent by subject, or date of death, or date of data cut-off.

Generally only the safety data (including adverse events, laboratory results, vital signs, ECG, ECOG PS, concomitant medications and etc.) reported during the safety observation period will be analyzed and summarized, unless otherwise specified in this plan.

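### The SAP safety window runs 30 days past last dose on cabozantinib but stops at last dose on placebo, so planned adverse-event differences tend to overstate the cabozantinib excess; SAP 9.3 also ends its numerator and person-time on different dates

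*Combined protocol and SAP*

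**What the plan says.** **Windows.** SAP 4.6 ends the cabozantinib safety observation period at the "earlier of the date of last dose of cabozantinib +30 days, or date of withdrawal of consent by subject", with death and data cut-off as further caps. Crossover cabozantinib also gets 30 days. The placebo period ends at the "earlier of the date of last dose of placebo, or date of withdrawal of consent by subject, date of death"; the day before open-label cabozantinib starts and the data cut-off also cap it. SAP Table 4 agrees: "Earlier of the date of last date of exposure to cabozantinib+30 days, or date of withdrawal of consent by subject" for cabozantinib, "Earlier of the last date of exposure to placebo, or date of withdrawal of consent by subject, date of death" for placebo. Neither place gives a reason.

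**Collection.** Protocol 8.1 makes no distinction by arm: events after consent and "through 30 days after the date of the decision to discontinue study treatment are to be recorded by the investigational site". Protocol 5.4.1 adds a safety visit: "Subjects who discontinue from study treatment will return to the site 30 (+14) days after the date of the decision to discontinue study treatment". Note c of protocol Table 20-1 also collects AEs up to 30 days after the decision to stop blinded treatment, and foresees gaps of more than 30 days before crossover dosing.

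**Use.** SAP 9.1 tabulates only treatment-emergent AEs with onset inside the window; SAP 9.5.2, 9.6.2, 9.7 and 9.8 apply the same filter to laboratory, vital sign, ECOG and ECG data. On these counts the SAP plans AE odds ratios, relative risks and risk differences. It also plans an AE table screened at an excess of 5% (all grades) or 2% (Grade 3/4), and a laboratory table screened at the same between-arm thresholds.

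**Rates.** SAP 9.3 divides AE episodes by the exposure of SAP 6.5, which ends at the decision date in both arms. SAP 8.4.7 uses person-years to the end of the safety observation period.

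**The concern.** A between-arm difference in incidence is interpretable only if events are counted over the same rule-defined period in both arms. Here a background event that starts a week after the last dose counts on cabozantinib and is dropped on placebo, although the site recorded both. For placebo subjects who cross over, an event between the last placebo dose and the first open-label dose falls in neither window.

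At stake are the tables that show which events are in excess on cabozantinib and by how much. SAP 9.3 is meant to adjust for exposure, but it inherits the unequal numerator and adds a second mismatch, because its denominator stops on a different date.

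**Working it through.** The documents give no figure for this point, so there is none to reproduce. The steps compare the definitions and then size the effect with no true difference between arms.

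**1. Can crossover drug explain the placebo rule?** Under an earlier-of rule that includes last placebo dose, the cap at open-label start minus one day binds only if open-label drug starts on or before the day of the last placebo dose. The cap is useful only if the placebo window runs past last dose. It would already keep crossover drug out of a +30-day window.

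**2. Spurious risk difference.** Inputs: T = 9 months (average treatment time, protocol 3.2) × 30.4375 = 274 days; on-treatment incidence p, the same in both arms; constant hazard h = −ln(1−p)/T, unchanged after last dose; all subjects stopped. The extra cabozantinib incidence is (1−p)(1−exp(−30h)):
- p = 10%: 1.03 points
- p = 20%: 1.93 points
- p = 50%: 3.65 points

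If the hazard halves after last dose: 0.52, 0.97 and 1.86 points. If no AE starts after last dose: 0.

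**3. Not everyone has stopped at the cut-off.** Data cut-off caps the window of a subject still on drug. Take a PFS event as a proxy for stopping, with the plan's inputs: exponential, cabozantinib median 9.0 months, 15 months' accrual, cut-off at 20 months. Then λ = ln 2/9.0 = 0.0770 and follow-up is uniform from 5 to 20 months. The share with an event is 1 − [exp(−5λ) − exp(−20λ)]/(15λ) = 1 − (0.680 − 0.214)/1.155 = 0.60. Multiplying step 2 by 0.6 gives 0.62, 1.16 and 2.19 points.

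**4. Against the screens.** At 9 months with all stopped, the window alone reaches 2 points from a placebo incidence of about 21%, or about 42% if 60% have stopped. It never reaches 5 points. Since the 2-point screen applies to Grade 3/4 events, the rule mostly pushes terms already near a threshold across it.

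**5. SAP 9.3.** Section 9.3 states no onset cut-off; it follows from 4.6 and 9.1. With L days from last dose to decision, numerator days over denominator days are (T−L+30)/T on cabozantinib and (T−L)/T on placebo. At T = 274:
- L = 0: 1.109 vs 1.000, ratio 1.11
- L = 14: 1.058 vs 0.949, ratio 1.115
- L = 30: 1.000 vs 0.891, ratio 1.12

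At L = 0 with 60% stopped, 1 + 0.6 × 30/274 = 1.07; with a halved post-dose rate, about 1.05.

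**6. Laboratory data.** The post-treatment visit falls on decision +30 to +44, which is 15 permitted days. On cabozantinib at most 1 of 15 lies inside the window (L = 0), and none if L is 1 or more. On placebo none does. The scheduled visit is lost almost equally in both arms.

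**7. Internal consistency.** The overall AE summary in SAP 9.1 counts events within the safety observation period, exempting only rows marked as at any time. It also lists Grade 5 events up to 30 days after last dose in each arm. Read literally, the placebo row cannot extend past last dose.

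**The case against.** **The placebo rule may be deliberate.** A drug effect can outlast the last dose and a placebo effect cannot. That could justify a drug-attributable summary on one arm, but not a between-arm difference, where the placebo arm supplies the background rate. The SAP offers no such reason.

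**Unequal follow-up exists anyway.** With planned median PFS of 9.0 and 5.5 months, crude incidence already compares periods about 3.5 × 30.4375 = 107 days apart. This stands: the rule adds 30 days to an existing imbalance, and removing it does not equalise exposure.

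**SAP 4.6 allows exceptions, and several outputs escape.** Deaths in SAP 9.4, rows counted at any time and the listings are outside the concern. The Grade 5 rows can be read as carrying their own window; the literal conflict in SAP 9.1 remains but is secondary.

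**Larger numbers are tempting and not supported.** Rate ratios of 1.14 (9 months) or 1.27 (5.5 months) need a 56-day lag in every subject, which is the longest dose hold allowed without Sponsor approval. The 5.5-month case also gives cabozantinib subjects the placebo median PFS as exposure. One omitted placebo subject moves the ORR safety (O-Safety) population by 3.0 points (1/33), but that reflects about 33 subjects under any window.

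**A reader might also infer a material laboratory bias, or a hidden drug signal.** Step 6 argues against the first: what remains needs unscheduled tests or visits soon after last dose. The expected direction overstates cabozantinib toxicity, so the second does not follow.

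**Conclusion.** The asymmetry is explicit, appears in two places, and is at odds with the protocol's equal collection of AEs. If AEs start after last dose in both arms, the planned AE comparisons tend to overstate the cabozantinib excess. The ranges in steps 2, 3 and 5 rest on equal true rates, equal 9-month exposure and, for the headline figures, last dose on the decision date. The share stopped is a PFS-based proxy, since treatment may continue past progression or end earlier for toxicity. The documents do not give the number of subjects affected.

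The SAP 9.3 mismatch is a separate defect: its numerator and denominator end on different dates in both arms, except where the lag happens to cancel the difference. No formal safety test is planned, so no type I error is involved. This should be corrected in the next SAP amendment, with high confidence in the definitional fault and less in its size.

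**What to change.** - In SAP 4.6 and Table 4, end the placebo window at last dose +30 days, capped at consent withdrawal, death, data cut-off and open-label cabozantinib start minus one day.
- In SAP 9.3, end the AE count and the person-time on the same date, for example with the safety-observation-period person-years of SAP 8.4.7.

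Under the equal-exposure model this brings the risk difference to 0 and the rate ratio to 1.00. Both changes are needed. With 4.6 corrected alone, each 9.3 numerator still runs 30 days past its denominator (all stopped, L = 0). At an assumed 9 months on cabozantinib and 5.5 on placebo, the ratio would be (9.986/9)/(6.486/5.5) = 1.110/1.179 = 0.94, a bias the other way.

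The cost is SAP wording and one derived end date; all dates are already collected, and SAP 9.9 already foresees an amendment. Two small downsides remain: some off-drug observations enter the placebo tables, and placebo subjects who cross over within 30 days keep a shorter tail.

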#### **4.7 Definition of Prior, Concomitant, and Subsequent Therapy**

For the purpose of inclusion in summary tables, incomplete medication or radiation start and stop dates will be imputed as detailed in **Error! Reference source not found.** Based on imputed start and stop dates:

- Prior medications/radiation therapies are defined as medications with a stop date occurring before the date of first dose of blinded study treatment.
- Concomitant medications/radiation therapies are defined as medications that stop or continue on or after date of first dose day through the end of safety observation period.
- Concomitant and Subsequent non-radiation anticancer therapies/radiation therapies are defined as those that stop or continue on or after the date of randomization.

Medications/radiation therapies may be summarized as prior, concomitant and/or subsequent.

#### **4.8 Software**

All analyses will be conducted using SAS Version 9.3 or higher.

#### **4.9 Changes to Planned Analyses**

Substantive changes to the analyses described in the protocol or in approved versions of this plan will be fully documented in a revised version of the plan approved by the Sponsor prior conducting unblinded analyses.

Clarifications, minor corrections, and operational considerations necessary to accurately conduct the analyses that do not materially change the nature of the analysis will be documented in an addendum to this plan that will also be approved by the Sponsor prior to unblinding the study to conduct the analyses. Any analyses not documented in the SAP or the addendum will be considered exploratory.

Since Overall Survival (OS) is not a primary endpoint in this study, an exploratory analysis for Time to Second Disease Progression or Death (PFS2) has been incorporated upon recommendation of EU Regulatory agencies as an intermediate clinical endpoint.

## **5 STUDY POPULATION SUMMARIES**

### **5.1 Enrollment**

Subjects are defined to be enrolled at randomization. Enrollment will be summarized by country, site, and protocol version for the OITT and ITT populations.

### **5.2 Disposition**

Subject disposition will be summarized categorically and will include the number and percentage of subjects in the OITT, ITT and O-Safety and Safety populations.

The reasons for blinded study treatment discontinuation, open-label treatment discontinuation, discontinuation of radiographic follow-up and survival follow-up discontinuation will also be summarized categorically.

All screen failure subjects will be summarized with the reason for screen failure.

### **5.3 Demographic and Baseline Characteristics**

Summaries of demographics, stratification factors and baseline characteristics will be presented for subjects in the OITT, ITT and O-Safety and Safety populations.

[A] The demographic characteristics include:

- Age (continuous)
- Age category 1
  - 16 - < 18 years
  - $\geq 18$  years
- Age category 2
  - < 45 years
  - $\geq 45$  years
- Age category 3
  - < 75 years
  - $\geq 75$  years
- Age category 4

- < 65 years
  - ≥ 65 years
    - 65 to <75 years
    - 75 to <85 years
    - ≥85 years
- Sex
  - Male
  - Female
  - Not reported
- Ethnicity
  - Hispanic or Latino
  - Not Hispanic or Latino
  - Not Reported
- Race
  - American Indian or Alaska Native
  - Asian
  - Black or African American
  - Native Hawaiian or Other Pacific Islander
  - White
  - Not Reported
  - Other
- Geographic Region
  - Asia
  - North America (USA/Canada)
  - Europe
  - Rest of the world

Note for this study birth date is not collected but age in years is collected at informed consent.

[B] Categorical summaries of the following stratification factors will be presented as recorded (a) in the IRT during randomization (b) on the CRF (c) cross tabulation of the 2 stratification factors per IRT (d) cross tabulation of the 2 stratification factors per CRF:

- Receipt of prior Lenvatinib (Yes, No)
- Age at informed consent (≤ 65 years, > 65 years)

[C] Baseline characteristics include:

- Height in centimeters (cm) – descriptive statistics
- Weight in kg – descriptive statistics
- Body mass index (BMI) in kg/meter, calculated as (weight in kg\*1000)/(Height in cm) –descriptive summary:
- ECOG PS: 0, 1, Missing
- Smoking history - Categorical summary for subjects classified as Current, Former or Never will be presented
- Alcohol use – Categorical summary for subjects classified as Current, Former or Never will be presented

#### **5.4 Medical History**

General medical history data will be coded per MedDRA and a subject data listing will be provided.

#### **5.5 Cancer History and Current Disease Status**

Cancer history and current disease characteristics data collected on the cancer history CRF will be summarized categorically or with descriptive statistics as appropriate. The following summaries are planned for the OITT, ITT and O-Safety and Safety populations:

- Diagnosis of DTC by histology or cytology (Yes, No)
- Diagnosis of DTC subtypes (Papillary thyroid carcinoma [PTC], Follicular thyroid carcinoma [FTC])
- Variants of PTC by histology (follicular variant, tall cell, columnar cell, cribriform-morular, solid, oxyphil, Warthin-like, trabecular, tumor with nodular fasciitis-like stroma, Hürthle cell variant of papillary carcinoma, poorly differentiated)
- Variants of FTC by histology (Hürthle cell, clear cell, insular, and poorly differentiated)
- Time in years to randomization since initial diagnosis of DTC as identified by histology or cytology (Note: Incomplete diagnosis dates will be imputed as detailed in **Error! Reference source not found.**)

- Time in months to randomization since last recurrence of DTC as identified by histology or cytology
- TNM staging at initial diagnosis, last recurrence and current evaluation of DTC
- Summaries for tumor assessment at screening per Investigator and BIRC are:
  - Extent of disease per target/non-target lesions
    - Bone
    - Important visceral sites
      - Lungs
      - Liver
    - All other sites
      - Incidence of all other sites will be individually reported
  - Number of target lesions (1, 2,  $\geq 3$ )
  - Number of non-target anatomic sites (1, 2,  $\geq 3$ )
  - Has measurable disease (Yes, No)

